Study HU-9001 were modeled using the DiliSym™ proprietary software that is currently the focus of a collaboration between the U.S. Food and Drug Administration (FDA) and The Hamner Institutes for Health Sciences [17]. This analysis indicated that subjects given entolimod had a pattern of minor hepatocyte loss and recovery similar to that observed in healthy subjects receiving commercially available heparin drug products (e.g., heparin, dalteparin, enoxaparin, adomiparin). Other laboratory abnormalities associated with entolimod administration were asymptomatic hyperglycemia and transient hypophosphatemia. All of these laboratory abnormalities were perceived to be transient and self-limiting, have no serious clinical implications, and require no monitoring or intervention. Such effects were seen following administration of IL-6 in patients with cancer [18] and, thus, are likely secondary consequences of entolimod-mediated induction of this cytokine.

Transient decreases in blood pressure and increases in pulse rate observed in Studies HU-7014/HU-9001 were also likely the result of entolimod-mediated IL-6 induction [19]. Most of the changes in blood pressure were within the normal range and were imperceptible to subjects, although a minority of study participants did describe dizziness and orthostatic syncope occurred in 1 subject. For those subjects that developed blood pressures below the normal range, the time to return to normal averaged ~6 hours, indicating that hypotension following entolimod administration is typically not long lasting. No elevations of serum creatinine or blood urea nitrogen (BUN) consistent with renal hypoperfusion were evident in any subject. Observations of hypotension were managed at the investigator's discretion in both Studies HU-7014 and HU-9001. Consequently, such changes were addressed inconsistently, with neither the minimum absolute blood pressure nor the maximum decrease from baseline necessarily prompting an investigator decision to administer intravenous (IV) fluids. Only 13 of 150 subjects (8.7%) received IV fluids and only 1 subject (0.6%) was given IV dopamine; the rationale for administering a pressor agent to this subject was unclear since they only had transient asymptomatic Grade 2 hypotension and were discharged normotensive the following day.

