4.2 Exclusion Criteria

Study candidates who meet any of the following criteria within 28 days prior to entolimod administration will not be eligible for participation in this study:

1. Receipt of any other vaccines within the past 30 days prior to enrollment
2. Acute illness within the last 7 days without systemic signs and symptoms including fever > 99.5
3. History of hypersensitivity to the flu vaccine or its components (including gelatin, formaldehyde, octoxinol, thimerosal, and chicken protein).
4. History of Guillain Barré syndrome (GBS)
5. History of bleeding disorders
6. Medical contraindication to treatment with vaccine as indicated by a history of autoimmune disease, immune deficiency, or hypersensitivity to other vaccines.
7. Unstable major cardiovascular, renal, endocrine, immunological or hepatic disorder
8. Systolic blood pressure (SBP) < 110 mmHg or orthostatic hypotension [>20 mmHg fall in SBP or >10 mmHg fall in diastolic blood pressure (DBP) with standing] at the time of screening.
9. Evidence of an ongoing systemic bacterial, fungal, or viral infection (including upper respiratory tract infections) (within 14 days prior to entolimod administration). **Note:** *Subjects with localized fungal infections of skin or nails are eligible.*
10. Baseline vital signs with \geq Grade 2 abnormalities
11. Significant cardiovascular disease (e.g., myocardial infarction, arterial thromboembolism, cerebrovascular thromboembolism, venous thromboembolism) within 6 months prior to study drug administration; symptomatic dysrhythmias or unstable dysrhythmias requiring

medical therapy; angina requiring therapy; symptomatic peripheral vascular disease; New York Heart Association Class 3 or 4 congestive heart failure; or uncontrolled Grade ≥ 3 hypertension (diastolic blood pressure ≥ 100 mmHg or systolic blood pressure ≥ 160 mmHg) despite antihypertensive therapy.

- a. Significant screening ECG abnormalities, including unstable cardiac arrhythmia requiring medication, atrial fibrillation, 2nd-degree atrioventricular (AV) block type II, 3rd degree AV block, or Grade ≥ 2 bradycardia (within 14 days prior to entolimod administration).
- 12. Inadequate hepatic function (within 14 days prior to entolimod administration):
 - a. Serum alanine aminotransferase (ALT) $\geq 3 \times$ upper limit of normal (ULN) (Grade ≥ 1).
 - b. Serum aspartate aminotransferase (AST) $\geq 3 \times$ ULN (Grade ≥ 1)

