Recommendations with regard to specific types of concomitant therapies, supportive care, diet and other interventions are provided in the protocol. To minimize variations in supportive care, the recommended supportive care agents (e.g., loperamide, granisetron) should be used unless there is a medical rationale in a specific subject for use of an alternative product.

Anti-inflammatory or Antipyretic Drugs or Corticosteroids

Anti-inflammatory or antipyretic drugs may not be administered prophylactically. Thereafter, subjects may receive ibuprofen, 400 mg orally, as needed every 4 to 6 hours in response to constitutional symptoms, fever or malaise occurring following study drug administration. Other nonsteroidal anti-inflammatory drugs (NSAIDs) may be substituted as medically necessary. Post-entolimod use of acetaminophen, 650 mg orally as needed every 4 to 6 hours, may be used in response to constitutional or pyretic symptoms if medically necessary, but use of acetaminophen is not encouraged given its potential for adverse hepatic effects.

The use of systemic, topical, inhaled, or enteric corticosteroids during screening or on Day 1 should be avoided given that such drugs may confound interpretation of safety and pharmacodynamic responses in subjects on this study. However, such drugs are permitted after study drug administration if a subject develops an intercurrent condition that require corticosteroid therapy.

Support for Hypotension

In the event that a subject experiences hypotension (SBP <90 mm Hg or DBP <60 mm Hg; a > 20 mm Hg drop in SBP or > 10 mm Hg drop in SBP with symptoms at any time after administration of study drug or with orthostatics) it may be managed according to standards of

care until the SBP is ≥ 90 mmHg and the DBP is ≥ 60 mmHg on ≥ 2 determinations obtained ≥ 1 hour apart [or until BP approaches within 10% of baseline (pre-study drug values) with resolution of symptoms]. It should be emphasized that a subject's clinical condition, rather than blood pressure alone, should be the primary basis for any intervention or medical decision-making.

- As much as possible, subjects should be kept at rest following study drug administration.

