- A subject requiring use of the bathroom should be evaluated for orthostatic changes. If the blood pressure is stable upon standing, and if the subject has no symptoms, the subject may ambulate to the bathroom, but study personnel should ensure the subject's safety. If there is a clinically significant drop in systolic blood pressure, or the subject complains of lightheadedness upon standing, the subject should be encouraged to use an emesis basin, urinal, bedpan, or bedside commode, as appropriate for the circumstances.
- For any hypotension more significant than minor dizziness, treatment should follow standard clinic protocol.

7 Statistical Plan

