10.2 Auditing and Inspecting

The investigator will permit study-related monitoring, audits, and inspections by the IRB, the sponsor, and government regulatory agencies, of all study related documents (e.g. source documents, regulatory documents, data collection instruments, study data etc.). The investigator will ensure the capability for inspections of applicable study-related facilities (e.g. pharmacy, diagnostic laboratory, etc.).

Participation as an investigator in this study implies acceptance of potential inspection by government regulatory authorities and applicable compliance offices.

11 Ethical Considerations

This study will be conducted according to United States government regulations and Institutional research policies and procedures.

This protocol and any amendments will be submitted to the Mayo Clinic Institutional Review Board (IRB), in agreement with local legal prescriptions, for formal approval of the study. The decision of the Mayo Clinic IRB concerning the conduct of the study will be made in writing to the sponsor-investigator before commencement of this study.

All subjects for this study will be provided a consent form describing this study and providing sufficient information for subjects to make an informed decision about their participation in this study. This consent form will be submitted with the protocol for review and approval by the IRB for the study. The formal consent of a subject, using the Approved IRB consent form, will be obtained before that subject undergoes any study procedure. The consent form will be signed by

the subject or the subject's legally authorized representative, and the individual obtaining the informed consent.

12 Study Finances

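### The post-dose hypotension trigger names systolic pressure for both drop limits and has no diastolic-drop limit, so some symptomatic or standing diastolic falls are missed (minor)

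*Combined protocol and SAP*

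**What the plan says.** The passage Support for Hypotension (Supportive Care, after Table S-1) gives two kinds of trigger for managing low blood pressure after dosing.

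- **Absolute floors:** "hypotension (SBP <90 mm Hg or DBP <60 mm Hg".
- **Drops:** "a > 20 mm Hg drop in SBP or > 10 mm Hg drop in SBP with symptoms at any time", continuing "after administration of study drug or with orthostatics".

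A subject who meets the trigger may be managed to standard of care until one of two recovery conditions holds. Either SBP is at least 90 and DBP at least 60 on two or more readings an hour or more apart, or pressure is back within 10% of baseline and symptoms have resolved. The same paragraph says that a subject's "clinical condition, rather than blood pressure alone, should be the primary basis for any intervention or medical decision-making".

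On walking to the bathroom, the protocol says: "If the blood pressure is stable upon standing, and if the subject has no symptoms, the subject may ambulate to the bathroom". The next sentence restricts the subject if there is a clinically significant systolic fall or a complaint of lightheadedness. It does not mention diastolic pressure.

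Exclusion criterion 8 (Section 4.2) uses the same two numbers differently: "orthostatic hypotension [>20 mmHg fall in SBP or >10 mmHg fall in diastolic blood pressure (DBP) with standing". It has no symptom requirement.

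Orthostatic pressures are taken at all visits (Table S-1, footnote q), and in every participant before discharge on the dosing day (Section 6.2).

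**The concern.** A rule with a 20 mm Hg limit and a 10 mm Hg limit, both on systolic pressure, looks like a transcription slip, because the protocol's own orthostatic definition assigns the 10 mm Hg limit to diastolic pressure. If so, one arm of the intended trigger is absent from the operative text, and staff following it literally would not act on a diastolic fall until DBP dropped below 60.

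What is at stake is consistent safety management in the hours after dosing. All subjects are 65 or older, and decreased blood pressure is a named potential risk (Section 1.6). In the earlier healthy-subject studies hypotension was handled at the investigator's discretion, "with neither the minimum absolute blood pressure nor the maximum decrease from baseline necessarily prompting an investigator decision to administer intravenous (IV) fluids" (Section 1.4.2.1). A written trigger helps to reduce that kind of inconsistency. Section 1.4.2.2 describes post-dose hypotension as generally without symptoms, although in cancer patients given repeated doses of 5 to 40 µg. Standing readings without symptoms therefore deserve attention as well as complaints.

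**Working it through.** The plan gives no figure to reproduce. The check is a logic test of the printed trigger.

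**Definitions.** S is reference SBP minus current SBP, and D is reference DBP minus current DBP. The reference is the pre-dose reading, or the reading before standing for an orthostatic measurement. Q is the qualifier at the end of the sentence.

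**Three ways to read the qualifier.**

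- A: symptoms or a standing reading qualify only the 10 mm Hg limit. Trigger = floor, or S > 20, or (S > 10 and Q).
- B: symptoms or a standing reading qualify both limits. Trigger = floor, or (S > 10 and Q). The 20 mm Hg limit then adds nothing.
- C: symptoms are required throughout, including on standing. The 20 mm Hg limit again adds nothing.

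Under A the 20 mm Hg limit adds only falls that are neither symptomatic nor orthostatic. Only A gives the printed pair a working two-tier meaning. Under B and C the redundancy itself points towards a slip.

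**The gap.** If S is 10 or less, neither drop limit can be met under any reading. A fall with D > 10 is then missed whenever DBP is at least 60 and SBP at least 90.

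**Where it starts.** D > 10 with current DBP of at least 60 requires a reference DBP above 70. From 70 or below, the same fall takes DBP under 60 and the floor catches it. In whole mm Hg, the missed values run from 60 to (reference − 11):

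| Reference DBP | Missed current DBP |
|---|---|
| 71 | 60 only |
| 80 | 60 to 69 |
| 85 | 60 to 74 |
| 90 | 60 to 79 |

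If reference SBP is at least 110, then S of 10 or less leaves SBP at 110 − 10 = 100 or more, so the SBP floor cannot help. The 110 is an assumption here: exclusion 8 applies it at screening, which may be up to 28 days before dosing.

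**Examples (illustrative baselines).**

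- Standing, no symptoms, 130/80 to 125/65: S = 5, D = 15. The printed trigger is not met under A, B or C, yet D > 10 on standing meets the orthostatic definition in exclusion 8. With a DBP term added under the existing qualifier, it is caught under A and B. It is still missed under C.
- Dizzy, not standing, 130/85 to 122/72: S = 8, D = 13. The printed trigger is not met under any reading. With the DBP term it is caught under all three.

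**Adding versus replacing.** Adding DBP only enlarges the trigger, so no case caught now is lost. Replacing the second SBP by DBP loses qualified SBP falls of 11 to 20 when D is 10 or less and both floors are respected. For example, 130/85 to 118/80 with dizziness (S = 12, D = 5) is caught as printed and missed after replacement.

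**The case against.** The strongest reply is that the change would do little in practice. Every gap case has SBP of at least 90 and DBP of at least 60, which are already the values in the first recovery condition, so triggering would mainly add a repeat reading. Vital signs are in any case repeated at 2, 4 and 6 hours, with orthostatic readings before discharge. Management is permissive and clinical condition comes first. The ambulation step requires stable pressure and no symptoms, and hypotension beyond slight dizziness follows standard clinic protocol. Section 1.6 says similar doses have not been associated with adverse reactions. The blood-pressure experience in Section 1.4.2.1 comes from doses of 2 to 50 µg in subjects aged 18 to 55. The printed text can also stand as a two-tier systolic rule, and a screening criterion and a care trigger need not match.

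Most of this stands, and it limits the severity. It does not supply the missing limit. The clinical-condition clause helps least where there are no symptoms, and the restricting sentence in the ambulation step names only systolic pressure. The requirement for stable pressure on standing gives partial cover.

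Three stronger readings are tempting but unsupported. A reader might infer that the slip is certain; the two-tier reading prevents that. A reader might infer that symptomatic subjects are left without care; the clauses above show otherwise. A reader might infer harm to the safety endpoint, dose-limiting toxicity assessment or stopping rules; the documents tie none of these to this trigger. Nor is it right to confine the gap to symptomatic subjects, because on the natural reading the closing words extend the trigger to standing readings.

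**Conclusion.** The point holds as a minor defect in operative safety text. The trigger names SBP for both drop limits and has no diastolic-drop limit. The second SBP is probably meant to be DBP, but this is an inference from exclusion 8.

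The missed cases are diastolic falls of more than 10 mm Hg with DBP at least 60, SBP at least 90 and an SBP fall of 10 or less, from a reference DBP above 70. They include symptomatic subjects. They also include standing falls without symptoms, provided the closing words are read as an alternative to symptoms. No incidence can be given, because the documents report no rate of such falls at 1 to 10 µg in this age group. The benefit of correction is limited to more consistent post-dose management.

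**What to change.** - In Support for Hypotension, add DBP to the 10 mm Hg limit without removing SBP: more than 20 mm Hg in SBP, or more than 10 mm Hg in SBP or DBP. Keep the existing closing qualifiers in full, including the orthostatic one. Wording that stopped at symptoms could delete a trigger now in the text.
- Ask the medical team to confirm the rule and to state whether the qualifier also covers the 20 mm Hg limit and whether a standing fall counts without symptoms.
- In the ambulation step, refer to a systolic or diastolic drop.

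The downside is a slightly broader trigger, which will take in some standing diastolic falls without symptoms. The cost is a line or two of text plus medical confirmation. Amendments go to the IRB (Section 11), so this can travel with the next one.

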7.1 Sample Size Determination

A sample size of 25 per arm provides 90% power to detect a doubling (100% increase) in geometric mean influenza antibody titer A/H1N1 based on a one-sided two-sample t-test at alpha level 0.15. This calculation assumes a coefficient of variation of 2.0 for A/H1N1. Under the assumption of smaller coefficient of variation for A/H3N2 and B antibody titers of 1.4, 25 per arm provides 90% power to detect an 80% increase in these antibody titers at alpha level 0.15. Thus, we plan to enroll 25 to each arm, for a total sample size of 100. We anticipate greater power under the ANCOVA approach, adjusted for baseline levels of the titer.

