The distribution of antibody titers (A/H1N1, A/H3N2, B) during follow up is anticipated to be skewed based on reporting in prior studies and a log-transformation will be applied to these outcomes. Antibody titers are measured at multiple time points in the first week after treatment, 4 weeks, 2 months, 6 months, and 12 months. A hierarchical mixed-effects regression model will be fit separately for the 3 endpoints, adjusting for the baseline/screening observation of the titer (an analysis of covariance (ANCOVA) approach). The model will include random subject-specific intercepts and model time as discrete. The primary outcome comparison is a contrast analysis of the outcome at 4 weeks comparing each entolimod dose to placebo. As the overall aim of this study is to assess safety and identify potential efficacy of entolimod, especially the dose most likely to succeed in Phase III study, we apply a one-sided test at alpha level 0.15 to each dose comparison (vs. placebo) and antibody titer combination, without multiplicity adjustment. The primary analysis will be conducted using the modified intent-to-treat analysis dataset.

Secondary Hypotheses: Secondary and exploratory endpoints require a variety of standard statistical methods.

Key secondary endpoints include the frailty indices, measures of physical function (6 minute walk test and grip strength), and quality of life (QOL). Frailty indices are measured at 2, 6, and 12 months and QOL measured at each study visit. For these outcomes, linear mixed effects models will assess the relationship between randomized arm and outcomes over time. Discrete times will be considered corresponding to the study visit and secondary analyses may consider continuous linear time (constant slope over time) for changes in the outcome. For these outcomes, the 12 month observation is the primary comparison.

Upper respiratory infections, including influenza, will be recorded over the follow up period. We anticipate the total number of these will be infrequent. Thus, we compare the outcome of any infection (vs. no infection) across randomized arms using a Pearson chi-square test or Fisher's exact test. Secondary approaches may consider analysis of the ordinal count of the number of infections, analyzed using a trend test.

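### Section 7.1 claims 90% power for its one-sided t-test, but the stated inputs, with the standard log-normal conversion of the CVs, give about 81% (A/H1N1) and 83% (A/H3N2 and B)

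*Combined protocol and SAP*

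**What the plan says.** Section 7.1 (Sample Size Determination) rests the choice of 25 per arm, 100 in total, on two power statements for a one-sided two-sample t-test at alpha 0.15:

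- A/H1N1: "A sample size of 25 per arm provides 90% power to detect a doubling (100% increase) in geometric mean influenza antibody titer A/H1N1". On variability: "This calculation assumes a coefficient of variation of 2.0 for A/H1N1".
- A/H3N2 and B, with a CV of 1.4: "25 per arm provides 90% power to detect an 80% increase in these antibody titers at alpha level 0.15".

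The section closes: "We anticipate greater power under the ANCOVA approach, adjusted for baseline levels of the titer". It gives no correlation between baseline and week-4 titer, and it does not say how the CVs were turned into log-scale SDs.

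Section 7.2 (Statistical Methods) confirms the scale and the comparison. For the titers, "a log-transformation will be applied to these outcomes". The primary comparison is a contrast of each dose with placebo at 4 weeks, and "we apply a one-sided test at alpha level 0.15 to each dose comparison (vs. placebo) and antibody titer combination", unadjusted for multiplicity. The analysis model is baseline-adjusted: "A hierarchical mixed-effects regression model will be fit separately for the 3 endpoints, adjusting for the baseline/screening observation of the titer".

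**The concern.** Section 7.1 names the test, its sidedness, alpha, group size, effects and CVs, so the power can be recomputed once the CVs are put on the log scale. With the usual conversion it falls 7 to 9 percentage points short of 90%, too much for rounding.

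This paragraph is the only justification for 25 per arm. The trial screens doses for a later phase III study and has already relaxed alpha to one-sided 0.15. A reader faced with a non-significant dose-by-titer comparison will lean on the stated 10% type II error, and for the stated test the true figure is nearly double that. This is not the chance of missing a dose, because the plan has no rule for combining the three titers.

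**Working it through.** **Inputs** (Section 7.1; log scale and per-dose contrast from Section 7.2)

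- n = 25 against 25, one-sided alpha 0.15, t-test with 48 degrees of freedom
- A/H1N1: ratio 2.0, CV 2.0
- A/H3N2 and B: ratio 1.8, CV 1.4

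**Step 1: log-scale SD.** One assumption is needed, that the CV describes the untransformed, log-normal titer. Then SD = sqrt(ln(1 + CV²)).

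- A/H1N1: sqrt(ln 5.00) = 1.2686
- A/H3N2 and B: sqrt(ln 2.96) = 1.0417

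**Step 2: noncentrality.** ncp = ln(ratio) / SD × sqrt(25/2).

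- A/H1N1: 0.6931 / 1.2686 × 3.5355 = 1.932
- A/H3N2 and B: 0.5878 / 1.0417 × 3.5355 = 1.995

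**Step 3: power.** The critical value is t(0.85; 48) = 1.048. Power is the probability that a noncentral t exceeds it.

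| | Stated | Noncentral t | Normal approximation | Simulation, 200,000 trials |
|---|---|---|---|---|
| A/H1N1 | 90% | 81.2% | 81.5% | 81.2% |
| A/H3N2 and B | 90% | 82.8% | 83.1% | 82.8% |

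Type II error is 18.8% and 17.2%, that is 1.88 and 1.72 times the stated 10%.

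**Step 4: what would give 90%.** Changing one quantity at a time:

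| | A/H1N1 | A/H3N2 and B |
|---|---|---|
| Log SD (equivalent CV) | 1.051 (1.42) | 0.891 (1.10) |
| Detectable ratio at n = 25 | 2.31 | 1.99 |
| n per arm at the stated effect and CV | 37 | 35 |

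**Step 5: attempts to reproduce the 90%.**

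| Reading | A/H1N1 | A/H3N2 and B |
|---|---|---|
| Error df from all four arms (96) | 81.3% | 83.0% |
| Two-sided alpha 0.15 | 68.2% | 70.4% |
| CV used directly as log SD | 57.2% | 67.0% |
| SD = sqrt(ln(1 + CV)), CV not squared | 90.1% | 87.9% |
| SD = ln(1 + CV) | 88.1% | 90.7% |
| Three doses pooled, 75 against 25 | 90.7% | 91.9% |

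The last three come close. Two use a formula that is not the log-normal relation, and neither reaches 90% for both CVs. Pooling the doses does reach it, but it contradicts the per-arm basis of Section 7.1 and the per-dose contrast in Section 7.2.

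**Step 6: the planned ANCOVA.** As a two-arm approximation, multiply the log SD by sqrt(1 − ρ²), where ρ is the correlation of baseline with week-4 log titer, and use 47 df. The documents give no ρ, so it is assumed here over a range:

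| Assumed ρ | A/H1N1 | A/H3N2 and B |
|---|---|---|
| 0.3 | 83.6% | 85.1% |
| 0.5 | 88.1% | 89.5% |
| 0.7 | 95.1% | 95.9% |

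Power reaches 90% at ρ of about 0.56 and 0.52.

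**Step 7: loss by week 4.** Section 7.1 makes no allowance for it. With assumed losses to 24, 22 or 20 evaluable per arm, t-test power is 80%, 78% and 75% (A/H1N1) and 82%, 79% and 77% (A/H3N2 and B).

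**The case against.** Three points can be made for the plan.

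- **The conversion is inferred.** Section 7.1 does not give a log SD or say that titers are log-normal, so 81% and 83% hold under the usual conversion and not by the text alone. That qualifier stands. But the formula used is the ordinary one when the effect is a ratio of geometric means, and neither of the other conversions that come close reaches 90% for both CVs.
- **The 90% may have been computed for another comparison.** Pooling the three doses against placebo gives more than 90% for both with the CVs and conversion unchanged. This is a plausible origin and should be checked. It does not rescue the sentence, because the plan compares each dose separately.
- **The t-test is not the primary analysis.** The baseline-adjusted model should have more power, and with a correlation of about 0.56 (A/H1N1) or 0.52 (A/H3N2 and B) it would reach 90%. In a screening trial, 81% to 83% may also be acceptable. Both are fair, and they mean that the trial has not been shown to be too small. But Section 7.1 assigns the 90% to the t-test and describes ANCOVA as a further gain, so ANCOVA cannot be the source of the figure as written.

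**Conclusion.** The concern holds. Under the standard log-normal conversion, the t-test in Section 7.1 has 81.2% power for a doubling in A/H1N1 and 82.8% for an 80% increase in A/H3N2 and B, per dose-by-titer comparison, against 90% stated.

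The result rests on the CVs being those of the untransformed titer and on all 25 per arm being evaluable. The documents do not show where the error lies: it could be the power figure, the CVs, their conversion or the comparison that was powered. For the planned ANCOVA, power could lie below or above 90%, and the documents do not settle which. As written, 90% is supported for neither analysis. The statement should be corrected; the sample size need not change on this ground.

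**What to change.** Keep 25 per arm. First establish how the 90% was obtained, including whether the doses were pooled. Then revise Section 7.1 in one of three ways:

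1. **If the CVs stand** (including where the 90% came from pooling), state about 81% power for a doubling in A/H1N1 (CV 2.0) and about 83% for an 80% increase in A/H3N2 and B (CV 1.4), by one-sided t-test at alpha 0.15. Equivalently, state 90% power for increases of about 2.3-fold and 2.0-fold.
2. **If the CVs or their conversion were misreported**, correct them and give the log SDs used. About 1.05 and 0.89 would support 90%.
3. **If 90% was meant for the ANCOVA**, say so and state the assumed correlation between baseline and week-4 log titer, about 0.56 (A/H1N1) and 0.52 (A/H3N2 and B), with its basis.

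In each case, add that power is per dose and per titer, and before any loss by week 4.

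The cost is wording in Section 7.1. Patient numbers, alpha and analysis are unchanged. Under option 1 the stated power becomes less favourable.
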